6.3.2. Blinding of Site Personnel Until the 1-Month Postdelivery Visit

In this observer-blinded study, the study staff receiving, storing, dispensing, preparing, and administering the study interventions will be unblinded. All other study and site personnel, including the investigator, investigator staff, and maternal participants, will be blinded to study intervention assignments. In particular, the individuals who evaluate maternal participant safety will be blinded. Because the BNT162 RNA-based COVID-19 vaccine candidate and placebo are different in physical appearance, the study intervention syringes will be administered in a manner that prevents the maternal study participants from identifying the study intervention type based on its appearance.

The responsibility of the unblinded dispenser and administrator must be assigned to an individual or individuals who will not participate in the evaluation of any maternal study participants. Contact between the unblinded dispenser and maternal study participants and unblinded administrator and maternal study participants should be kept to a minimum. The remaining site personnel must not know study intervention assignments.

In the event of a Quality Assurance audit, the auditor(s) will be allowed access to unblinded study intervention records at the site(s) to verify that randomization/dispensing has been done accurately.

To allow administration of BNT162b2 to maternal participants who originally received placebo, site staff will be unblinded to individual participants' original study intervention allocation at the 1-month postdelivery visit.

6.3.3. Blinding of Site Personnel Prior to the 1-Month Postdelivery Visit

To allow administration of BNT162b2 to maternal participants who originally received placebo, site staff will be unblinded to individual participants' original study intervention allocation at the 1-month postdelivery visit. Prior to unblinding maternal participants at the 1-month postdelivery visit, this is an observer-blinded study. The study staff receiving, storing, dispensing, preparing, and administering the study interventions will be unblinded. All other study and site personnel, including the investigator, investigator staff, and maternal participants, will be blinded to study intervention assignments until the 1-month postdelivery visit for each participant. In particular, the individuals who evaluate maternal participant safety prior to unblinding maternal participants at the 1-month postdelivery visit will be blinded.

Because the BNT162 RNA-based COVID-19 vaccine candidate and placebo are different in physical appearance, the study intervention syringes will be administered in a manner that prevents the maternal study participants from identifying the study intervention type based on its appearance during the blinded portion of the study.

The responsibility of the unblinded dispenser and administrator must be assigned to an individual or individuals who will not participate in the evaluation of any maternal study participants prior to the maternal participant being unblinded. Contact between the unblinded dispenser and blinded maternal study participants and unblinded administrator and blinded maternal study participants should be kept to a minimum. The remaining site personnel must not know study intervention assignments until the maternal participant is unblinded at the 1-month postdelivery visit.

In the event of a Quality Assurance audit, the auditor(s) will be allowed access to unblinded study intervention records at the site(s) to verify that randomization/dispensing has been done accurately.

6.3.4. Blinding of the Sponsor

The study team will be unblinded to the participant's study intervention allocation when maternal participants complete the 1-month postdelivery visit. Prior to unblinding the maternal participants at the 1-month postdelivery visit the majority of sponsor staff will be blinded to study intervention allocation. All laboratory testing personnel performing serology assays will remain blinded to study intervention assigned/received. The following sponsor staff, who will have no part in the blinded conduct of the study, will be unblinded (further details will be provided in a data blinding plan):

- Those study team members who are involved in ensuring that protocol requirements for study intervention preparation, handling, allocation, and administration are fulfilled at the site will be unblinded for the duration of the study (eg, unblinded study manager, unblinded clinical research associate).
- Unblinded clinician(s) who are not direct members of the study team and will not participate in any other study-related activities will review unblinded protocol deviations.
- An unblinded team supporting interactions with, and analyses for, the DMC (see [Section 9.6](#)). This will comprise a statistician, programmer(s), and a medical monitor and/or a clinical scientist who will review cases of severe COVID-19 as they are received, and will review AEs at least weekly for additional potential cases of severe COVID-19 (see [Section 8.2.4](#)).
- An unblinded submissions team will be responsible for preparing unblinded analyses and documents to support regulatory activities that may be required while the study is ongoing. This team will only be unblinded at the group level and not have access to individual participant assignments. The programs that produce the summary tables will be developed and validated by the blinded study team, and these programs will be run by the unblinded DMC team.

6.3.5. Breaking the Blind

The IRT will be programmed with blind-breaking instructions. In case of an emergency, the investigator has the sole responsibility for determining if unblinding of a maternal participant's vaccine assignment is warranted. Participant safety must always be the first consideration in making such a determination. If the investigator decides that unblinding is warranted, the investigator should make every effort to contact the sponsor prior to unblinding a maternal participant's vaccine assignment unless this could delay further management of the participant.

If a maternal participant's vaccine assignment is unblinded, the sponsor must be notified within 24 hours after breaking the blind. The date and reason that the blind was broken must be recorded in the source documentation and CRF.

The study-specific IRT reference manual and IP manual will provide the contact information and further details on the use of the IRT system.

Instructions on how to unblind participants ahead of administration of BNT162b2 to placebo recipients will be provided separately: this unblinding will NOT be performed in the IRT.

6.4. Study Intervention Compliance

When maternal participants are dosed at the site, they will receive study intervention directly from the investigator or designee, under medical supervision. The date and time of each dose administered in the clinic will be recorded in the source documents and recorded in the CRF. The dose of study intervention and maternal study participant identification will be confirmed at the time of dosing by a member of the study site staff other than the person administering the study intervention.

6.5. Concomitant Therapy

6.5.1. Prohibited During the Study – Maternal Participants

Receipt of the following vaccines and medications during the time periods listed below may exclude a maternal participant from the per-protocol analysis from that point onwards, and may require vaccinations to be discontinued in that participant; however, it is anticipated that the maternal participant would not be withdrawn from the study (see [Section 7](#)). Medications should not be withheld if required for a maternal participant's medical care.

- Unless considered medically necessary, no vaccines other than study intervention should be administered within 14 days before and 7 days after each study vaccination, including seasonal and pandemic influenza vaccines.
- Receipt of chronic systemic treatment with known immunosuppressant medications within 60 days before enrollment through conclusion of the study.
- Receipt of systemic corticosteroids (≥ 20 mg/day of prednisone or equivalent) for ≥ 14 days is prohibited from 28 days prior to enrollment through Visit 3.

- Receipt of blood/plasma products or immunoglobulins within 60 days before enrollment through conclusion of the study.
- Receipt of any other (nonstudy) coronavirus vaccine at any time prior to or during study participation is prohibited.
- Prophylactic antipyretics and other pain medication to prevent symptoms associated with study intervention administration are not permitted. However, if a maternal participant is taking a medication for another condition, even if it may have antipyretic or pain-relieving properties, it should not be withheld prior to study vaccination.

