Numerous COVID-19 vaccines are currently in development globally, and several candidate COVID-19 vaccines (eg, mRNA vaccines and adenovirus-vectored vaccines expressing the S protein) have been shown to be efficacious in the prevention of COVID-19 in clinical studies and are now available under temporary or emergency authorizations.²¹ BNT162b2, an RNA-based COVID-19 vaccine given as a 2-dose series administered 21 days apart, was shown to be safe and effective in a Phase 1/2/3 study and has received authorizations for temporary or emergency use or marketing authorizations in multiple countries and has been fully licensed for use in individuals 16 years of age and above in the US as of 23 August 2021.^{22,23}

On 22 September 2021, based on safety and immunogenicity data from approximately 300 immunocompetent adult booster-dose recipients from Study C4591001, the FDA issued the EUA for a single booster dose of BNT162b2 30 μg for 1) individuals 65 years of age and older; 2) individuals 18 through 64 years of age at high risk of severe COVID-19; and 3) individuals 18 through 64 years of age whose frequent institutional or occupational exposure to SARS-CoV-2 puts them at high risk of serious complications of COVID-19, including severe COVID-19.²⁴ On 19 November 2021, the FDA amended the EUA, authorizing use of a single booster dose for all individuals 18 years of age and older after completion of primary vaccination with an FDA-approved COVID-19 vaccine.²⁵ On 09 December 2021, the FDA again amended the EUA to authorize the use of a single booster dose for administration to individuals 16 and 17 years of age at least 6 months after completion of primary vaccination with BNT162b2.²⁶ In addition, a booster dose of the vaccine is authorized in the EU and other countries, with recommendations for populations varying based on local health authority guidance.^{27,28}

The currently available safety and immunogenicity data are presented in the BNT162 IB.

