4. STUDY DESIGN

4.1. Overall Design

This will be a global Phase 2/3, randomized, placebo-controlled, observer-blind study in approximately 350 healthy pregnant women 18 years of age or older vaccinated during their 24 to 34 weeks' gestation. This study will evaluate the safety, tolerability, and immunogenicity of 2 doses of BNT162b2 or placebo administered 21 days apart. The Phase 2 portion of the study will include approximately 200 pregnant women randomized 1:1 to receive BNT162b2 or placebo (saline) during their 27 to 34 weeks' gestation. Safety data through 7 days after the second dose (where Day 1 is the day of vaccination) for all Phase 2 participants will be reviewed by the Pfizer IRC. The Phase 3 portion of this study will assess the safety, tolerability, and immunogenicity of BNT162b2 in approximately 150 pregnant women enrolled during their 24 to 34 weeks' gestation who will be randomized in a 1:1 ratio to receive BNT162b2 or placebo (saline). Phase 3 will proceed after the first 200 maternal participants have been enrolled in Phase 2. Maternal participants who originally received placebo will receive BNT162b2 at defined time points as part of the study.

Enrollment in this study was terminated on 25 Oct 2021 with approximately 350 participants enrolled. Enrollment was terminated due to enrollment challenges into a placebo-controlled study as a result of universal recommendations for COVID-19 vaccination of pregnant women and the increased global availability of COVID-19 vaccines. Enrollment numbers within this protocol have been modified accordingly.

The study is observer-blinded, as the physical appearance of the investigational vaccine and the placebo may differ. The participant, investigator, study coordinator, and other site staff will be blinded through the 1-month postdelivery visit for each maternal participant. At the study site, only the dispenser(s)/administrator(s) are unblinded.

Each maternal participant will participate in the study for approximately up to 10 months depending on the vaccine group to which she was randomized. Her infant will participate in the study for approximately 6 months. The study duration will be approximately 14 months.

For each placebo recipient who will go on to receive BNT162b2 and follow a new visit schedule ([Section 1.3.2](#)), she will participate in the study for up to 7 months, and her infant will participate in the study for approximately 6 months.

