4. ANALYSIS SETS (POPULATIONS FOR ANALYSIS)

Analysis populations are defined for the statistical analysis of safety, immunogenicity, and efficacy results in the table below. For the specified criteria in each population definition that are not associated with unblinded information (randomized vaccine or vaccine actually received), data for all participants will be assessed to determine if participants meet the criteria for inclusion in each analysis population prior to unblinding and releasing the database, and the classifications will be documented per standard operating procedures.

Population	Description
Enrolled	All participants who have a signed ICD.
Randomized	All participants who are assigned a randomization number in the IWR system.
Evaluable immunogenicity (maternal)	All participants who 
 are eligible and randomized; receive 2 doses of the vaccine to which they are randomized, with Dose 2 received within the predefined window (19-42 days, inclusive, after Dose 1); have at least 1 valid immunogenicity result within an appropriate window 1 month after Dose 2 (28-42 days, inclusive, after Dose 2); and have no other important protocol deviations as determined by the clinician.
Dose 1 evaluable immunogenicity (maternal)	All participants who 
 are eligible and randomized; receive Dose 1 of the vaccine to which they are randomized; have at least 1 valid immunogenicity result within an appropriate window 1 month after Dose 1 (19-23 days, inclusive); and have no other important protocol deviations as determined by the clinician.
Evaluable immunogenicity (infant)	All infant participants born to evaluable immunogenicity maternal participants and have no important protocol deviations as determined by the clinician.
All-available immunogenicity (maternal)	All randomized participants who receive at least 1 dose of the study intervention with at least 1 valid and determinate immunogenicity result after vaccination.
All-available immunogenicity (infant)	All infant participants born to all-available immunogenicity maternal participants.
Evaluable efficacy (maternal)	All eligible randomized participants who receive all vaccination(s) as randomized, with Dose 2 received within the predefined window (within 19-42 days after Dose 1), and have no other important protocol deviations as determined by the clinician on or before 7 days after Dose 2.

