All-available efficacy (mITT) (maternal)	Dose 1 all-available efficacy: All randomized participants who receive at least 1 vaccination. Dose 2 all-available efficacy: All randomized participants who complete 2 vaccination doses.

Population	Description
All-available efficacy (mITT) (infant)	All infant participants born to Dose 1 all-available maternal participants.
Safety (maternal)	All randomized participants who receive at least 1 dose of the study intervention.
Safety (infant)	All infant participants born to maternal participants who receive at least 1 dose of the study intervention.

The important protocol deviations will be determined by the medical monitor. An important protocol deviation is a protocol deviation that, in the opinion of the sponsor's clinician, would materially affect assessment of immunogenicity/efficacy, eg, participant receipt of a prohibited vaccine or medication that might affect immune response or a medication error with suspected decrease in potency of the vaccine. The sponsor's clinician will identify those participants with important protocol deviations that result in exclusion from analysis populations before any unblinded analysis is carried out.

For all the immunogenicity endpoints, the analysis will be based on the evaluable immunogenicity population. An additional analysis will be performed based on the corresponding all-available immunogenicity population if there is over 10% difference in sample size between the all-available immunogenicity population and the evaluable immunogenicity population. Participants will be summarized according to the vaccine group to which the maternal participants were randomized.

The safety analyses will be based on the safety population. Participants will be summarized by vaccine group according to the study interventions the maternal participants actually received.

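### The supplementary all-available antibody tables keep samples drawn after a prohibited nonstudy COVID-19 vaccine, which can inflate 6-month BNT162b2 titers and placebo delivery and cord IgG

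*Protocol*

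**What the plan says.** Protocol 6.5.1 sets the prohibition: "Receipt of any other (nonstudy) coronavirus vaccine at any time prior to or during study participation is prohibited". Its stated consequence for analysis is that receipt "may exclude a maternal participant from the per-protocol analysis from that point onwards"; the woman is expected to stay in the study.

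SAP 4 then defines two kinds of antibody set.

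- **Evaluable.** Participants must "have no other important protocol deviations as determined by the clinician". The text below the table gives receipt of a prohibited vaccine that might affect immune response as an example of such a deviation. The infant set follows the mother. All immunogenicity endpoints are based on these sets.
- **All-available.** The maternal set is "All randomized participants who receive at least 1 dose of the study intervention with at least 1 valid and determinate immunogenicity result after vaccination". The infant set is "All infant participants born to all-available immunogenicity maternal participants".

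The second kind is conditional: "An additional analysis will be performed based on the corresponding all-available immunogenicity population if there is over 10% difference in sample size". Protocol 9.4.1 is looser and says only that such an analysis may be done if the difference is large enough.

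SAP 6.2.2.1.1 (maternal antibody over time) and 6.2.4.1.1 (infant IgG) list both sets against the same Section 2.1 estimands. SAP 2.1 places those estimands in a hypothetical setting of protocol adherence. In both sections the entry for intercurrent events covers only values below the LLOQ and missing data.

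Two background statements bear on exposure. Protocol 2.2.1 records a US decision of 19 November 2021 "authorizing use of a single booster dose for all individuals 18 years of age and older after completion of primary vaccination". Protocol 4.1 says enrollment stopped on 25 October 2021 because it was hard to enroll into a placebo-controlled study, given "universal recommendations for COVID-19 vaccination of pregnant women and the increased global availability of COVID-19 vaccines".

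**The concern.** A titer measured after a nonstudy coronavirus vaccine is not a response to the randomized product alone. In the all-available sets nothing removes it, so it counts toward the arm to which the woman was randomized. At 6 months after delivery, a booster in the BNT162b2 arm would be read as persistence of the primary series. At delivery and in cord blood, outside vaccination of a placebo woman would lift what should be an unvaccinated reference.

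The all-available run is the planned companion to the evaluable analysis. If the two differ, the reader needs to know whether the difference comes from women who missed the 1-month sample or from titers raised by another vaccine. As defined, the all-available tables mix the two.

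**Working it through.** The plan gives no uptake rate and no fold change, so there is no figure of its own to reproduce. The check has four steps.

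**1. Will the all-available analysis run?** Evaluable status needs a valid result 28-42 days after Dose 2 (SAP 4). Visit 4 is not held if delivery comes first (Protocol 1.3.1, footnote). With Dose 2 at 21 days, a woman delivering at week G reaches day 28 after Dose 2 only if her gestational age at Dose 1 is at most G - (21 + 28)/7 = G - 7 weeks. Assume gestational age at Dose 1 is uniform over 27-34 weeks in Phase 2 (200 women) and 24-34 weeks in Phase 3 (150 women):

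| Delivery (assumed) | Cut at Dose 1 | Phase 2 share missed | Phase 3 share missed | Pooled |
|---|---|---|---|---|
| 40 wk | 33 wk | 1/7 = 14.3% | 1/10 = 10.0% | (200 × 0.143 + 150 × 0.100)/350 = 12% |
| 39 wk | 32 wk | 2/7 = 28.6% | 2/10 = 20.0% | 25% |
| 38 wk | 31 wk | 3/7 = 42.9% | 3/10 = 30.0% | 37% |

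These women still have a delivery sample, so they stay in the all-available set. The other evaluable criteria widen the gap further. The 10% trigger is therefore likely to be met, though at 40 weeks the margin is small.

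**2. Can a booster precede the 6-month sample?** Visit 8 is 160-200 days after delivery. Days from Dose 2 to Visit 8 = (week of delivery - week of Dose 1) × 7 - 21 + 160 to 200.

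- Shortest (Dose 1 at 34 weeks, delivery at 37): 21 - 21 + 160 = 160 days.
- Longest (Dose 1 at 24 weeks, delivery at 40): 112 - 21 + 200 = 291 days.

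For a woman given Dose 1 on 25 October 2021 and delivering at 40 weeks, Visit 8 falls 42 + 160 = 202 to 112 + 200 = 312 days later, between 15 May and 2 September 2022. That is after the adult booster decision. A woman dosed at 34 weeks before about 1 May 2021 (19 November minus 202 days) could have Visit 8 before it. Exposure is feasible for many women but not for all.

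**3. How large is the distortion?** A geometric mean is the exponential of a mean log. If a share p of samples is raised F-fold, the mean log rises by p × log F and the geometric mean is multiplied by F^p. Both p and F are assumptions.

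| Time point and arm | p | F | Factor |
|---|---|---|---|
| Any | 0 | any | 1.00 |
| 6 months, BNT162b2 | 10% | 5 | 1.17 |
| 6 months, BNT162b2 | 20% | 10 | 1.58 |
| 6 months, BNT162b2 | 30% | 20 | 2.46 |
| Delivery or cord, placebo | 2% | 100 | 1.10 |
| Delivery or cord, placebo | 5% | 100 | 1.26 |
| Delivery or cord, placebo | 10% | 100 | 1.58 |

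**4. What is outside its reach?** The primary GMR uses the BNT162b2 arm 1 month after Dose 2 (SAP 3.1.2), which leaves little time for another vaccine. Placebo mothers move to Visits 101-103 (Protocol 1.3.2), which include no 6-month sample, so the maternal 6-month point concerns the BNT162b2 arm only.

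**The case against.** The strongest reply is that the headline results are already protected. Every immunogenicity endpoint is based on the evaluable sets, and SAP 4 names a prohibited vaccine as a reason to exclude. A reader might infer that the main persistence, delivery and cord results are inflated; the documents do not support that, although the exclusion rests on clinical judgment. This part of the reply stands and confines the point to supplementary tables.

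A second reply is that an all-available set is meant to be inclusive, and that SAP 2.1 ties the protocol-adherent estimand to the evaluable sets. This stands in part. However, SAP 6.2.2.1.1 and 6.2.4.1.1 offer the all-available sets for the same estimands, and no separate target that would count other vaccines is declared. Showing results both ways meets the objection.

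Third, a reader might infer that outside vaccination was common. Protocol 4.1 speaks of recruitment difficulty and vaccine availability. It says nothing about enrolled women being vaccinated elsewhere, and no uptake figure appears. The booster date is a US one in a global study, and Protocol 2.2.1 says recommendations elsewhere vary. This stands: the effect is possible, not shown.

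Fourth, a reader might conclude that a disagreement between the two analyses could not be interpreted at all. That goes too far. SAP 6.6.2.1 reports exclusions from each population with reasons by arm, and SAP 6.6.4 tabulates concomitant vaccines after Dose 1 by arm. Neither places the vaccine relative to each blood sample, so these outputs help but do not separate the affected titers.

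**Conclusion.** The gap is real and limited. Both all-available immunogenicity sets lack any rule for samples taken after a nonstudy coronavirus vaccine, and the analysis on them will probably be run. In those tables the 6-month GMT/GMC in the BNT162b2 arm can be inflated, and placebo delivery and cord IgG can be raised, by F^p. Modest assumptions give 10% to 17%, larger ones a doubling or more, and zero uptake gives no effect. The trigger estimate rests on uniform gestational age at Dose 1 and delivery at 38-40 weeks; the size rests on p and F, for which the documents offer nothing. The evaluable results have their own exclusion route, all endpoints are descriptive, and the primary GMR is little affected. It is worth fixing because the change is cheap, not because a main conclusion is at risk.

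**What to change.** In SAP 4, 6.2.2.1.1 and 6.2.4.1.1, add: *In the all-available immunogenicity analyses, results from samples collected after the first nonstudy coronavirus vaccine are excluded from that point onwards. The mother's vaccination date applies to her own samples; maternal receipt before delivery applies to cord and infant samples. Earlier results are kept. The number excluded is shown by arm and time point.* If the sponsor prefers the fully inclusive set, show results with and without these samples.

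This matches the time-based consequence in Protocol 6.5.1 and the way SAP Appendix 2 ends COVID-19 surveillance at the first important violation. It needs SAP wording and one programmed date check. Nonstudy vaccinations are recorded under Protocol 6.5.3 and at the visits in Protocol 1.3.1, which cover both arms through delivery.

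The cost is fewer samples, mainly at 6 months. With a share b excluded, the interval width on the log scale grows by √(1/(1 - b)): 1.05 at 10% and 1.12 at 20%.
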